- Each participant will have approximately 2 weeks, or as much time as they need, to decide upon their participation after initial discussion with the research team doctor or nurse. Consent will be obtained by a participating medical doctor or nurse within the research team.. Translators are provided by the NHS Trust for non-English speaking participants. Only adults able to understand the nature of adipose tissue biopsy will be recruited.
- We will use the UHS clinical code database containing patients with a diagnosis of NAFLD. This information will be sought from the UHS Information Team in accordance with UHS NHS policy.

Detail of randomisation procedure

- Participants will be block randomized according to standardized procedures (computerized randomization) by a person from within University Hospital Southampton or the University of Southampton who is not connected to the INSYTE study. Investigators will be blinded as to treatment allocation until cessation of the trial.
- Stratified randomization to either trial medication (synbiotic or placebo) will be used.

Participant compliance

Participants will be asked to return all used and unused sachets at their next study clinic visit and their final clinic visit. Compliance will be assessed as percentage of sachets used.

- Non-compliance will be defined as missed usage of sachets for more than 6 months (53) (consecutively) during the whole study and or missed usage of sachets for 3 months (consecutively) before the end of the study.
- We will consider as compliant, participants who have had one or two courses of broad spectrum antibiotics during the study period. Participants will continue the synbiotic treatment during the antibiotic therapy and we will extend the synbiotic treatment for at least 1 month (i.e. 12+2 months of active therapy) before the final visit.

If there is indication that participants are non-compliant with trial treatment during the trial they will be withdrawn.

Detail of follow-up of non-compliant subjects & withdrawal of subjects

- Participants will be withdrawn if they develop a serious chronic illness that affects their liver condition.
- Participants will be withdrawn if they require treatment with a known hepatotoxic drug.
- Participants will be withdrawn if they have more than two courses of antibiotic therapy that is
 recognized to influence gut microflora during the study.

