To address this scientific question we will undertake an exploratory pilot study in $\sim n = 12/50$ participants from the 50 participants randomised to synbiotic and $\sim 12/50$ participants from the group randomised to placebo. Participants will be invited to undergo a stepped hyperinsulinaemic clamp with deuterated glucose to assess hepatic and whole body insulin sensitivity. We will undertake these studies in collaboration with [name] from the University of Surrey with whom we have collaborated previously in undertaking studies of this nature.

Methods for postprandial study day

Proposed methodologies to investigate:

- fasting and postprandial hepatic DNL (fatty acid and cholesterol) in VLDL-TG using deutrated water (²H₂O)
- bile acid and cholesterol metabolism using deutrated water (²H₂O)
- postprandial hepatic fatty acid partitioning using [U-¹³C]palmitate and measuring incorporation into ¹³C-VLDL-TG, and 13C appearing in 3-hydroxybutyrate (3-OHB) in deproteinised plasma, breath CO₂ and hepatic urea (to measure ¹³CO₂- i.e. hepatic CO₂)

Hepatic fatty acid partitioning in NAFLD: the effect of pre- and pro-biotics

We will also investigate hepatic fat synthesis [hepatic *de novo* lipogenesis (DNL)] and hepatic fat breakdown (oxidation) (130) in a subset of individuals from the control approximately (n=12) and intervention approximately (n=12) before and after the randomised intervention. We will use stable (i.e. non-radioactive) isotopes to probe human metabolism, particularly that of the liver.

The purpose of this investigation is to obtain data in a sub-group of participants to address the question of whether there is any relationship between rate of hepatic DNL and postprandial fat oxidation, in people with a histological diagnosis of NAFLD in relation to hepatic fat quality as measured by magnetic resonance imaging (MR) and diagnostic liver biopsy. Additionally, in this sub-group study, we will test whether the therapeutic intervention has affected hepatic DNL and postprandial oxidation.

De novo hepatic fatty acid synthesis

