- ii. To assess change in biomarkers with synbiotic treatment
- iii. To assess change in gut microbiota composition with synbiotic treatment

Secondary outcomes:

- i. Liver fibrosis determined by transient elastography
- ii. Insulin and glucose concentrations and hepatic insulin sensitivity
- iii. Microvascular function
- iv. Plasma cardiovascular risk markers
- v. Adipose tissue and blood markers of metabolism and inflammation
- vi. De novo lipogenesis
- vii. Satiety and satiety factors

Study site: University Hospital Southampton

Sample size and power

There is little published literature to date upon which to base a sample size calculation to test the effects of the synbiotic treatment on the primary end points. However, the study has been powered on the basis of the expected change in the key primary end point of a change in liver fat.

Based on the mean \pm SD of liver fat content in the sample of people with NAFLD who we recruited for our current randomised trial testing the effects of a n-3 fatty acid intervention in NAFLD in the WELCOME study (the Wessex Evaluation of fatty Liver and Cardiovascular markers in NAFLD with OMacor thErapy study); we estimate that the sample size would give 85% power to detect a 40% decrease in liver fat with the synbiotic intervention (allowing for 14% drop out). In the WELCOME study conducted over a longer period of intervention, 5% of the randomised cohort withdrew between randomisation and end of study measurements. In the WELCOME study the mean percentage fat content was 28.5%. Thus it is reasonable to expect that after treatment with the synbiotic, the mean percentage fat content would be 20% (giving a 30% decrease in liver fat). Liver fat content will be measured by MRS spectroscopy and this technique can reproducibly detect liver fat content as low as 5%.

One recent publication in people with NAFLD testing the effect of a synbiotic over 24 weeks in a small study showed a 69% decrease in liver fat (53).

Randomisation procedures

Patients will be randomised according to standardized procedures (computerized randomisation by a person from within University Hospital Southampton or the University of Southampton who is not connected to the INSYTE study). Stratified randomisation by age, sex and sub-study to trial medication or placebo will be used.

Data monitoring and interim analyses

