Detailed analysis and publication of baseline data will be undertaken prior to trial completion by Profs, [name] and [name] and other investigators in discussion with the research nurses and BRC statistician. An independent data monitoring committee (IDMC) has not been set up for this trial, so there are no planned interim analyses of outcome data.

Procedures for data checking

Data will be checked for transcription and validation errors. Prior to any statistical analysis, all variables will be checked for number of missing values, impossible and improbable values. Impossible and improbable values for continuous variables will be defined by clinical opinion, other improbable values, defined as being more than three standard deviations from the mean, will also be checked. Errors in categorical variables will be identified as those with values missing from given terms in the Data

Dictionary. Inconsistencies will be referred to a named investigator by the data management team. Descriptive statistics will be calculated for all variables and distributional assumptions checked.

Trial analysis

Description of baseline data

All important variables collected at baseline will be summarised by treatment group. For continuous variables; means and standard deviations will be calculated. Distributions will be assessed using histograms and the normality assumption will be tested. When the data are not normally distributed medians and percentiles will be used to summarise data. Number and percentage will be calculated for categorical and binary data.

Primary endpoint

Change in liver fat and biomarkers from randomisation to end of study.

1. Change in liver fat (measured by MRS or IPOP MRI)

2. Change in biomarkers:

a) ELF score which is calculated using the following algorithm:

Score= $-7.412 + (\ln(HA)*0.681) + (\ln(P3NP)*0.775) + (\ln(TIMP1)*0.494).$

b) NAFLD fibrosis score which is calculated using age, hyperglycemia, body mass index, platelet count, albumin and AST/ALT ratio.

c) CK18 M30 and M65 as markers of apoptosis and necrosis

3. Change in gut microflora assessed by 16S rRNA, FISH and qPCR

Change in liver fat from randomisation to end of study

Measurement

Magnetic resonance spectroscopy (MRS) and/or MRI (IPOP) imaging will be used to determine the amount of liver fat as a percentage of the whole liver. This will be performed at baseline and at the end of study visit.

Change in biomarkers

Measurement

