Biomarkers will be measured in plasma or serum or will be generated from an algorithm.

Change in gut microflora

Measurement

Gut microflora will be assessed by 16S rRNA, FISH and qPCR

Statistical analysis

There are three primary endpoints; change in liver fat, change in biomarkers and change in gut microflora.

For measurements of liver fat, biomarkers and gut microflora:

Multiple regression analysis will be used, with final visit measurement as the outcome, and baseline measurement and randomised treatment group as predictors.

For each measurement, a multiple regression analysis will also be performed adjusted for potential confounders.

Potential confounders include but are not limited to: Change in body weight

For all outcomes, the treatment effect with 95% confidence interval will be reported (regardless of whether statistical significance is met). This will allow discussion of whether the trial result is compatible with a clinically important effect.

When reporting results it will be acknowledged that care should be taken in interpreting results from several outcome measures, as some statistically significant findings are likely to result from chance alone; consequently, we will allow for multiplicity of testing when interpreting our results.

Analyses by intention to treat (ITT) and Per Protocol

Analyses will be undertaken by an intent-to-treat (ITT) analysis and per protocol.

1. The ITT analysis will include all patients with complete data (i.e. having baseline and end of study measurements) in the groups to which they were randomised (regardless of whether they were later found to be ineligible, a protocol violator, given the wrong treatment allocation or never treated). This analysis assumes that any missing data is missing at random (MAR), i.e. that there is no difference between missing and observed values, once adjusted for any baseline variables which predict for missingness.

In order to explore the effect of departures from the MAR assumption, sensitivity analyses will be performed (140).

This assumes that d= the mean of the missing data minus the mean of the observed data. Under MAR, d=0.

The value of d will then be varied in order to model different scenarios (i.e. that the patients who are lost to follow up have systematically worse outcomes), and we will report whether the significance of the main analysis is maintained in the sensitivity analysis.

All randomised participants will be accounted for in these analyses.

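### Randomisation is stratified by age, sex and sub-study, but the main regression for the primary outcomes omits all three: valid, with confidence intervals slightly too wide if the factors are prognostic

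*Protocol*

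**What the plan says.** **Randomisation.** Section VIII (Detail of randomisation procedure) states "Participants will be block randomized according to standardized procedures" and "Stratified randomization to either trial medication (synbiotic or placebo) will be used", without naming the factors. Appendix 1 (Randomisation procedures) names them: "Stratified randomisation by age, sex and sub-study to trial medication or placebo will be used". Block size and age bands are not given.

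**Main analysis.** Appendix 1 (Statistical analysis) gives one model for all three primary endpoints: "Multiple regression analysis will be used, with final visit measurement as the outcome, and baseline measurement and randomised treatment group as predictors".

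**Additional analysis.** The same section adds, for each measurement, a second regression adjusted for potential confounders: "Potential confounders include but are not limited to: Change in body weight". The list is open, but none of the stratification factors is on it.

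**Related details.** One of the primary biomarkers contains age: "NAFLD fibrosis score which is calculated using age, hyperglycemia, body mass index, platelet count, albumin and AST/ALT ratio". The lipogenesis work in Section IX.12 is done "in a subset of individuals from the control approximately (n=12) and intervention approximately (n=12) before and after the randomised intervention", and the clamp study there is of similar size.

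**The concern.** Stratified blocking makes the arms nearly equal on age, sex and sub-study, so the treatment difference varies less from trial to trial than under simple randomisation. A model without these factors does not see that gain. Whatever they explain beyond the baseline value stays in the residual variance, and the standard error is overstated. The test is then somewhat conservative, and precision that the design has already secured is not used. Balance is also only approximate, because the analysis takes participants with both measurements and withdrawn participants may be replaced during recruitment. The model terms would pick up what imbalance remains.

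At stake is a small amount of interval width and power. Bias and false-positive error are not affected.

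**Working it through.** **Inputs from the protocol.** 50 per arm, 14% dropout, difference 40%, SD 62%, two-sided 0.05 (Section VII); about 12 of 50 per arm in the sub-study (Section IX.12).

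**The plan's own figure.** Evaluable per arm: 50 × (1 − 0.14) = 43. Power = Φ(40/62 × √(43/2) − 1.96) = Φ(2.99 − 1.96) = 84.9%, which reproduces the stated 85%. The noncentral t version gives 84.1%. This calculation takes no account of baseline adjustment, so the powers below are higher.

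**Assumptions, because the protocol is silent.** Blocks of 4; two age bands × sex × sub-study (8 strata, 24 participants in the sub-study); 14 random dropouts, leaving n = 86; age and sex together explain a share R² of both the baseline and the final variance; r is the baseline-to-final correlation.

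**Closed form.** The share of residual variance that the factors explain after baseline is

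p = [R²/(1 − R²)] × (1 − r)/(1 + r).

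Leaving them out widens the interval by a factor of about 1/√(1 − p). Against this stands the cost of three extra terms (residual degrees of freedom 83 to 80, plus slight imbalance). With non-prognostic factors the simulated widths put that cost at 0.7499/0.7465 = 1.0046 for r = 0.5, 0.8256/0.8220 = 1.0044 for r = 0.3 and 0.6178/0.6151 = 1.0044 for r = 0.7.

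**Simulation.** 20,000 null and 20,000 alternative runs per setting, effect 40/62 SD, baseline in both models. Widths are in SD units.

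| r | R² | p | 1/√(1 − p) | Width without / with factors | Ratio | Power without / with |
|---|---|---|---|---|---|---|
| 0.3 | 5% | 2.8% | 1.014 | 0.8212 / 0.8134 | 1.010 | 87.2 / 87.6% |
| 0.3 | 10% | 6.0% | 1.031 | 0.8219 / 0.8007 | 1.026 | 87.5 / 88.6% |
| 0.3 | 20% | 13.5% | 1.075 | 0.8219 / 0.7682 | 1.070 | 87.8 / 90.9% |
| 0.5 | 5% | 1.8% | 1.009 | 0.7456 / 0.7426 | 1.004 | 92.5 / 92.5% |
| 0.5 | 10% | 3.7% | 1.019 | 0.7459 / 0.7356 | 1.014 | 92.8 / 93.1% |
| 0.5 | 20% | 8.3% | 1.044 | 0.7461 / 0.7178 | 1.039 | 92.8 / 94.0% |
| 0.7 | 5% | 0.9% | 1.005 | 0.6147 / 0.6147 | 1.000 | 98.4 / 98.3% |
| 0.7 | 10% | 2.0% | 1.010 | 0.6151 / 0.6120 | 1.005 | 98.4 / 98.4% |
| 0.7 | 20% | 4.4% | 1.023 | 0.6150 / 0.6042 | 1.018 | 98.5 / 98.7% |

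Dividing 1/√(1 − p) by the cost of about 1.0045 gives the simulated ratio in each row to within 0.1 point. At r = 0.5 and R² = 0/5/10/20%, the type I error is 5.1/4.9/4.6/4.3% for the planned model and 5.1/5.1/5.1/4.9% with the factors (Monte Carlo error about 0.15 points).

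**A second simulation** (8,000 runs per setting) took R² as the share of residual variance after baseline, with correlation 0.6. For 5/10/20% the planned interval is 2/5/11% too wide and its type I error is 4.1/4.2/3.6%; both estimators were unbiased. The figures are larger because 5 to 20% of residual variance is a stronger assumption: at r = 0.5, the R² values in the table correspond to only 1.8 to 8.3% of it.

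**NAFLD fibrosis score.** Write the score as c × age plus a remainder independent of age and of constant variance, with baseline-to-final correlation ρ < 1 in the remainder. The expected final score given baseline and age is then ρ × baseline + c(1 − ρ) × age + a constant. Age still predicts the final score after baseline adjustment, with coefficient c(1 − ρ). The documents give neither c nor ρ, and age bands would capture only part of this.

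**The case against.** The strongest reply is that nothing here is wrong. Baseline-adjusted regression is an accepted primary model, the protocol never promises to adjust for the strata, and Appendix 1 is only an outline. The open confounder list could admit age, sex and sub-study. The gain is also slight: at r = 0.5 with factors explaining 5 to 10% of variance, power rises by 0.0 to 0.3 points, and if the factors are not prognostic, adjusting loses 0.1 to 0.5 points. Age in the fibrosis score enters both baseline and final values, so much of it is already absorbed.

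Most of this stands, and it keeps the priority low. It does not remove the point. The outline does not leave the main model open: it writes out the predictors. The confounder model supplements that model and does not replace it. The fibrosis-score argument holds only for what age adds beyond baseline.

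One practical objection also stands. Section IX.12 describes two investigations, a clamp study and a lipogenesis study, without saying whether they use the same people. It also describes the clamp participants as drawn from those randomised. The visit table in Section X lists both tests at baseline, which supports sub-study status being known at randomisation, but a single yes/no term is an assumption.

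**Conclusion.** The concern holds as a small, conditional loss of precision. The stratification factors are stated and the main model omits them; the estimate remains unbiased and the type I error is at or below nominal. For factors explaining 5 to 20% of baseline and final variance, the planned interval is 0.4 to 3.9% too wide at r = 0.5, 0.0 to 1.8% at r = 0.7 and 1.0 to 7.0% at r = 0.3. The power gained by adjusting is at most 1.2, 0.2 and 3.1 points respectively. The mismatch and its direction are certain. The size rests on assumed prognostic strength, block size, age bands and random dropout, and may be close to zero.

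**What to change.** In Appendix 1 (Statistical analysis), state the main model for outcomes measured in the whole cohort (liver fat, biomarkers, gut microflora) as final measurement on treatment group, baseline measurement, age in the bands used for randomisation, sex, and sub-study participation coded as it was for randomisation (yes/no if there was a single sub-study stratum).

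For outcomes measured only in the sub-study (clamp, de novo lipogenesis), leave out the sub-study term, which is constant there, and do not carry age and sex over automatically. At n = 24 and r = 0.5, adding non-prognostic age and sex widens the interval by about 1.5% if the arms are balanced on them within the sub-study (1.491 to 1.513) and by about 5.8% if they are not (1.489 to 1.576).

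The cost is one line of text. With two age bands, the whole-cohort model uses three more degrees of freedom (86 − 3 = 83 falls to 86 − 6 = 80). If the factors turn out not to be prognostic, the interval is under 0.5% wider and power is 0.1 to 0.5 points lower. No new data are needed, since stratification factors must be known when a participant is randomised.

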1.1 Energy harvest

The energy harvest from nutrients is significantly affected by the composition of the intestinal microbiota. Several studies have been conducted to analyse the relationship between gut microbiota and body fatness, resulting in divergent observations. For example, Ley et al. showed that obese individuals and genetically obese ob/ob mice have a large proportion of *Firmicutes* and a low proportion of *Bacteroidetes* compared with lean controls (10;11). In contrast, Duncan et al. did not find a relationship between a high *Firmicutes/Bacteroidetes* ratio and obesity (12).

Gut microbiota dysequilibrium can cause a reduction of *Fasting-induced adipose factor* (Fiaf, Angiopoietin-like protein 4), a protein inhibitor of lipoprotein lipase (LPL) activity synthesised in brown and white fat, liver and intestine. Fiaf is an important control factor involved in triglyceride homeostasis, as it modulates energy absorption from the diet, and energy (lipid) storage in liver, muscle and adipose tissue (13;14). Backhed et al. described that the suppression of the intestinal expression of Fiaf by gut microbiota causes increased LPL activity that leads to an increased cellular uptake of fatty acids with consequent triglyceride accumulation in the muscle, adipocytes and liver. In the same study, conducted on animals and humans, Backhed showed higher serum levels of Fiaf in healthy individuals than in patients with type 2 diabetes (15). Overall, low level of Fiaf causes an excessive energy absorption, which leads to obesity and liver lipid storage with development of NAFLD.

B. thetaiotaomicron, a Gram-negative anaerobic bacterium present in the gut significantly affects monosaccharide uptake from the intestine (16). This bacterium degrades indigestible polysaccharides and increases fermentation, contributing to produce body fat accumulation, obesity and insulin resistance (17). Moreover, in the presence of Paneth cells, *B. thetaiotaomicron* increases the capillary density of the intestinal villus favouring monosaccharide absorption. The carbohydrate uptake from the gut, promotes delivery of monosaccharides to the liver which cause the up-regulation of sterol response element binding protein 1 (SREBP-1) and carbohydrate response element binding protein (ChREBP). These two factors induce the hepatic transcription of the genes encoding lipogenic enzymes, so promoting hepatic triglyceride production (15).

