A diet rich in fats is likely to result in higher levels of liver cholesterol, leading to an increased synthesis of bile acids. The consequences of this altered metabolism are the accumulation and impaired detoxification of secondary bile acids which are more hydrophobic and toxic than primary bile acids.

Secondary bile acids have the following two toxic effects:

- i. Increased intestinal permeability with decreased expression of tight junctions. This allows for transfer of endotoxin products (i.e. LPS from Gram negative bacterial membrane) from the intestine to the blood stream and thus to the portal vein and into the liver, causing inflammation and cytokine production (26;27).
- ii. Apoptosis of enterocytes and hepatocytes. The hydrophobicity of secondary bile acids allows for their interaction with the phospholipids in cell membranes of hepatocytes and enterocytes. Secondary bile acids can also travel to the cytosol inducing perturbations of the mitochondrial membrane. The alterations of the mitochondria stimulate the production of reactive oxygen species (ROS) that in turn enhance mitochondrial permeability and cause the release of cytochrome c and other factors that form the apoptosome, ultimately causing cellular apoptosis and necrosis (28).
- 1.3 Insulin resistance/satiety/intermediate metabolism

The gut microbiota modulates glycaemic homeostasis through the production of gut hormones. An imbalance in gut microbiota causes a decrease of enteroendocrine L cells, resulting in a decrease of serum levels of GLP-1, GLP-2 and PYY (29;30). This mechanism causes an impaired glucose control and an impaired satiety (31).

In the colon, dietary fibres (non-digestible carbohydrates) are fermented and converted by anaerobic bacteria (*inter alia* lactobacilli and bifidobacteria species) to form short-chain fatty acids (SCFAs). The ability of bifidobacteria to produce SCFAs is ascribed to the activity of their β -fructofuranosidase and the presence of cellular oligosaccharide uptake system (32).

Dietary fibres have the following effects:

- Bifidogenic effect. Dietary fibres are broken down in different ways by bifidobacteria and these different degradation mechanisms are responsible for metabolic competition among intestinal bacteria. Change in the composition of the gut microbiota has been associated with:
 a) decreased intestinal endotoxemia and LPS production; and b) decreased translocation of pathogenic bacteria (33).

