3.1 The action of probiotics

- i. Competitive exclusion of intestinal bacteria
- ii. Lower pH gradient in the intestine, thus promoting butyrate production and decreasing acetate concentration. This condition inhibits the growth of Gram-negative pathogenic bacteria (54).
- iii. Improvement of epithelial barrier function
- 3.2 The action of prebiotics
 - i. Increase of enteroendocrine L cells, resulting in increased serum levels of GLP-1, GLP-2 and PYY (29;30)
 - ii. Reduced plasma triglyceride levels, muscle lipid infiltration, adipose tissue mass and oxidative stress (30;55)
- iii. Reduced inflammation and improved immune function (56).

III. Detection and monitoring of fatty liver disease

Key to this study will be the use of non-invasive markers of liver function and of NAFLD disease severity. These tests utilizing serum markers of fibrosis are widely used in clinical practice in Europe. Numerous studies (57-69) have evaluated the two main markers, hyaluronic acid (HA) and collagen PIIINP peptide in patients with fatty liver disease (alcohol and non-alcohol related). Studies include a total of over 6000 subjects, of whom nearly 3000 had fat related disease aetiology. In those

studies where an area under the curve analysis (AUROC) was reported (70-72), the mean value was 0.91 compared with liver biopsy – acceptable diagnostic accuracy.

Algorithms have also been developed to generate a composite liver fibrosis score generated from concentrations utilizing HA and PIIINP, in combination with another marker TIMP-1 (73). It has been suggested that this approach may lead to an increase in specificity and sensitivity for diagnosing NAFLD. Others have also very recently developed algorithms based on less expensive simple biochemical tests, used in combination with simple anthropometry. For example, the clinical algorithm developed by Newcastle/Mayo group collaboration (74) uses age, glycaemia, BMI, albumin, platelet count and the AST/ALT ratio. This algorithm also has excellent sensitivity (77%) and specificity (96%) for detecting severe fibrosis.

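### The supplementary model adjusts for change in body weight as a confounder, but it arises after randomisation and may carry part of the treatment effect

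*Protocol*

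**What the plan says.** The relevant text is in the Protocol, section XI (Appendix 1), under the statistical analysis of the three primary endpoints: liver fat, biomarkers and gut microflora.

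- Main model: "Multiple regression analysis will be used, with final visit measurement as the outcome, and baseline measurement and randomised treatment group as predictors".
- Second model: "For each measurement, a multiple regression analysis will also be performed adjusted for potential confounders".
- The only covariate named for it, in an open-ended list: "Potential confounders include but are not limited to: Change in body weight".

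The same appendix makes the NAFLD fibrosis score one of the primary biomarkers: "NAFLD fibrosis score which is calculated using age, hyperglycemia, body mass index, platelet count, albumin and AST/ALT ratio".

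The background (section II) gives routes by which treatment could alter weight or fat mass:

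- Section 1.1 (energy harvest): "Overall, low level of Fiaf causes an excessive energy absorption, which leads to obesity and liver lipid storage with development of NAFLD".
- Section 1.3, on loss of gut hormones when the microbiota is disturbed: "This mechanism causes an impaired glucose control and an impaired satiety".
- Section 3.2, among the actions of prebiotics: "Reduced plasma triglyceride levels, muscle lipid infiltration, adipose tissue mass and oxidative stress".

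Satiety is also a secondary outcome (section VI). Nowhere is the second model described as a mediation or direct-effect analysis.

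**The concern.** A confounder of the treatment comparison has to influence, or share a cause with, allocation. Randomisation rules that out for any variable, and change in weight is not known until after allocation. The label is therefore wrong. If treatment changes weight and weight changes liver fat, conditioning on weight change takes out the part of the effect that runs through weight.

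What remains is not reliably a weight-independent effect either. Diet or physical activity could drive both weight change and liver fat. Conditioning on weight change then links treatment to those unmeasured causes and biases the coefficient further.

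Two primary measurements raise an extra difficulty. The NAFLD fibrosis score contains body mass index, so adjusting it for weight change comes close to conditioning on a component of the outcome. For the microbiota, section 1.1 places body fatness downstream of the bacteria, so the model would adjust an outcome for its own possible consequence.

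The stake is interpretation. Both estimates will be reported, and one is labelled as controlling confounding. A reader could take a smaller adjusted effect as the truer one, when the gap may be part of the benefit.

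**Working it through.** **Protocol inputs (section VII).** 50 per arm with 14% drop-out gives 50 × 0.86 = 43 per arm; difference 40%; SD 62%; two-sided alpha 0.05; stated power 85%.

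**Reproducing the stated power.** 40 / (62 × √(2/43)) = 40 / 13.37 = 2.99, and Φ(2.99 − 1.96) = 84.9% (84.1% by t-test). The stated 85% reproduces. This is context only; the point does not depend on it.

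**Units.** All effects below are on that 40%/SD 62% scale. They are not absolute percentage points of liver fat, since the mean quoted from the earlier trial is only 28.5%.

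**Assumptions not in the Protocol.** Baseline–final correlation 0.6; weight change explains 16% of the residual variance; true total effect 40.

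- Residual SD given baseline: 62 × √(1 − 0.6²) = 49.6.
- Slope per SD of weight change: √0.16 × 49.6 = 19.84.
- Expected weight-adjusted effect: 40 − 19.84 × (arm difference in weight change, in SD).

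Simulation of both regressions, 5,000 trials per scenario:

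| Arm difference in weight change (SD) | Formula | Simulated adjusted effect | Power of adjusted model |
|---|---|---|---|
| 0 | 40.0 | 40.0 | 98% |
| 0.1 | 38.0 | 38.0 | 96% |
| 0.2 | 36.0 | 35.9 | 95% |
| 0.3 | 34.0 | 34.0 | 92% |
| 0.5 | 30.1 | 30.4 | 84% |
| 1.0 | 20.2 | 20.2 | 44% |

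The main model returned 39.9 to 40.3 with power 95–96% in every scenario.

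**Sensitivity.** With the correlation varied over 0.4–0.8 and explained variance over 5–30%, the adjusted effect is 34–38 at 0.2 SD, 24–36 at 0.5 SD and 9–32 at 1 SD.

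**Unmeasured common cause.** Suppose half the slope (9.92) comes from a shared cause. At 0.5 SD the true weight-independent effect is 40 − 0.5 × 9.92 = 35, but the model still gives about 30.

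**Second parameterisation, also assumed.** Treatment lowers weight by 1–3 kg and each kg is worth 3–5 units. The total effect is −40, where minus means a fall in liver fat. The weight-adjusted estimate runs from about −37 to −25, and from about −35 to −21 with an added common cause. With no effect on weight it stays at about −40. The model without weight change gives about −40 throughout.

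**Precision.** When weight does not differ by arm, the 95% CI half-width in simulation is about 21.4 without weight change and 19.7 with it. The closed form agrees: 1.99 × 49.6 × √(2/43) = 21.3, and 1.99 × 49.6 × √0.84 × √(2/43) = 19.5.

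**The case against.** The strongest reply is that the primary inference is untouched. The baseline-plus-treatment model comes first, the adjusted model is additional, and all treatment effects are to be reported with confidence intervals, so the sound estimate will be visible beside the other. That stands, and it limits the seriousness of the point.

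The distortion also needs two conditions: the synbiotic must change weight, and weight must affect the outcome. The Protocol gives no figure for the first. Section 1.1 itself reports divergent findings on microbiota and body fatness. One of the two sources cited for reduced adipose mass is, by its title, a mouse study. Section 1.3 describes what a disturbed microbiota does, not what the synbiotic does to weight. So mediation is plausible, not established. If weight does not differ by arm, the adjusted model is slightly more precise, with power about 98% against about 96%. This stands too.

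Choosing baseline covariates is commonly left to a statistical analysis plan. But the Protocol is not silent here: it names a post-randomisation variable and calls it a confounder. Correcting a stated rule is different from asking for missing detail.

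**Conclusion.** The concern holds. The Protocol mislabels a post-randomisation variable as a confounder in a model planned for all primary measurements, and its own rationale makes that variable a plausible mediator. The main model is valid and unaffected.

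Under the assumptions shown, the understatement is negligible up to an arm difference of about 0.2 SD in weight change (36 instead of 40). It becomes material from about 0.5 SD (30, range 24–36) and large at 1 SD (20, range 9–32). No figure in the Protocol says where this trial would fall. The error should be corrected, but it does not threaten the main analysis.

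**What to change.** In Appendix 1:

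1. Remove change in body weight from the list of confounders.
2. Restrict the adjusted models to variables measured before randomisation, for example baseline weight or body mass index and the stratification factors already stated: "Stratified randomisation by age, sex and sub-study to trial medication or placebo will be used".
3. State that the model with baseline value and treatment group carries the conclusion.
4. Report change in body weight by arm as an outcome.
5. If a model with weight change is wanted, keep it as an exploratory mediation analysis and state its assumption of no unmeasured common cause of weight change and outcome.

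The cost is two or three sentences. Section X already schedules anthropometry at baseline, at 5–6 months and at follow-up. The weight-independent question moves to exploratory status. If weight turns out not to differ by arm, a little precision is given up (the half-widths of 21.4 against 19.7 shown above).
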